### 8.1.1.3. Maintenance Study

The primary objectives of the Maintenance Study are:

- To evaluate the efficacy of filgotinib as compared to placebo in establishing clinical remission by CDAI at Week 58
- To evaluate the efficacy of filgotinib as compared to placebo in establishing endoscopic response at Week 58

The key secondary objectives of the Maintenance Study are:

- To evaluate the efficacy of filgotinib as compared to placebo in establishing clinical remission by PRO2 at Week 58
- To evaluate the efficacy of filgotinib as compared to placebo in establishing clinical response by CDAI at Week 58
- To evaluate the efficacy of filgotinib as compared to placebo in establishing sustained clinical remission by CDAI at Weeks 10 and 58
- To evaluate the efficacy of filgotinib as compared to placebo in establishing 6-month corticosteroid-free remission by CDAI at Week 58
- To evaluate the efficacy of filgotinib as compared to placebo in establishing sustained clinical remission by PRO2 at Weeks 10 and 58
- To evaluate the efficacy of filgotinib as compared to placebo in establishing 6-month corticosteroid-free remission by PRO2 at Week 58

The other secondary objectives of the Maintenance Study are:

- To evaluate the safety and tolerability of filgotinib
- To assess the PK characteristics of filgotinib

**CCI** [REDACTED]

[REDACTED]

- To evaluate the efficacy of filgotinib as compared to placebo in establishing both clinical remission by PRO2 and endoscopic response (combined into a single end point on a patient level) at Week 58
- **CCI** [REDACTED]
- **CCI** [REDACTED]
- **CCI** [REDACTED]

- CCI [REDACTED]
- CCI [REDACTED]
- CCI [REDACTED]
- CCI [REDACTED]
- CCI [REDACTED]
- CCI [REDACTED]

#### 8.1.1.3.1. EU-Specific Objectives for the Maintenance Study

The EU-specific primary objectives of the Maintenance Study are:

- To evaluate the efficacy of filgotinib as compared to placebo in establishing clinical remission by PRO2 at Week 58
- To evaluate the efficacy of filgotinib as compared to placebo in establishing endoscopic response at Week 58

The EU-specific key secondary objectives of the Maintenance Study are:

- To evaluate the efficacy of filgotinib as compared to placebo in establishing clinical remission by CDAI at Week 58
- To evaluate the efficacy of filgotinib as compared to placebo in establishing sustained clinical remission by PRO2 at Weeks 10 and 58
- To evaluate the efficacy of filgotinib as compared to placebo in establishing both clinical remission by PRO2 and endoscopic response (combined into a single end point on a patient level) at Week 58
- To evaluate the efficacy of filgotinib as compared to placebo in establishing 6-month corticosteroid-free remission by PRO2 at Week 58

The EU-specific other secondary objectives of the Maintenance Study are:

- To evaluate the safety and tolerability of filgotinib
- To assess the PK characteristics of filgotinib

CCI [REDACTED]

[REDACTED]

[REDACTED]

[REDACTED]

[REDACTED]

[REDACTED]

[REDACTED]

[REDACTED]

[REDACTED]

[REDACTED]

[REDACTED]

**8.1.2. Primary Endpoints**

8.1.2.1. Cohort A Induction Study

- The proportion of subjects achieving clinical remission by CDAI at Week 10
- The proportion of subjects achieving endoscopic response at Week 10

8.1.2.1.1. EU-Specific Primary End points for the Cohort A Induction Study

- The proportion of subjects achieving clinical remission by PRO2 at Week 10
- The proportion of subjects achieving endoscopic response at Week 10

8.1.2.2. Cohort B Induction Study

- The proportion of subjects achieving clinical remission by CDAI at Week 10
- The proportion of subjects achieving endoscopic response at Week 10

8.1.2.2.1. EU-Specific Primary Endpoints for the Cohort B Induction Study

- The proportion of subjects achieving clinical remission by PRO2 at Week 10
- The proportion of subjects achieving endoscopic response at Week 10

8.1.2.3. Maintenance Study

- The proportion of subjects achieving clinical remission by CDAI at Week 58
- The proportion of subjects achieving endoscopic response at Week 58

8.1.2.3.1. EU-Specific Primary Endpoints for the Maintenance Study

- The proportion of subjects achieving clinical remission by PRO2 at Week 58
- The proportion of subjects achieving endoscopic response at Week 58

**8.1.3. Secondary Endpoints**

8.1.3.1. Cohort A Induction Study

The key secondary end points of Cohort A are:

- The proportion of subjects achieving clinical remission by PRO2 at Week 10
- The proportion of subjects achieving clinical response by CDAI at Week 10

The other secondary end point of Cohort A is:

- PK characteristics for filgotinib and its metabolite GS-829845

8.1.3.1.1. EU-Specific Secondary Endpoints for the Cohort A Induction Study

The EU-specific key secondary end points of Cohort A are:

- The proportion of subjects achieving clinical remission by CDAI at Week 10
- The proportion of subjects achieving both clinical remission by PRO2 and endoscopic response (combined into a single end point on a patient level) at Week 10

The EU-specific other secondary end point of Cohort A is:

- PK characteristics for filgotinib and its metabolite GS-829845

#### 8.1.3.2. Cohort B Induction Study

The key secondary end points of Cohort B are:

- The proportion of subjects achieving clinical remission by PRO2 at Week 10
- The proportion of subjects achieving clinical response by CDAI at Week 10

The other secondary end point of Cohort B is:

- PK characteristics for filgotinib and its metabolite GS-829845

#### 8.1.3.2.1. EU-Specific Secondary Endpoints for the Cohort B Induction Study

The EU-specific key secondary end points of Cohort B are:

- The proportion of subjects achieving clinical remission by CDAI at Week 10
- The proportion of subjects achieving both clinical remission by PRO2 and endoscopic response (combined into a single end point on a patient level) at Week 10

The EU-specific other secondary end point of Cohort B is:

- PK characteristics for filgotinib and its metabolite GS-829845

#### 8.1.3.3. Maintenance Study

The key secondary end points of the Maintenance Study are:

- The proportion of subjects achieving clinical remission by PRO2 at Week 58
- The proportion of subjects achieving clinical response by CDAI at Week 58
- The proportion of subjects achieving sustained clinical remission by CDAI at Weeks 10 and 58
- The proportion of subjects achieving 6-month corticosteroid-free remission by CDAI at Week 58
- The proportion of subjects achieving sustained clinical remission by PRO2 at Weeks 10 and 58
- The proportion of subjects achieving 6-month corticosteroid-free remission by PRO2 at Week 58

The other secondary end point of the Maintenance Study is:

- PK characteristics for filgotinib and its metabolite GS-829845

#### 8.1.3.3.1. EU-Specific Secondary Endpoints for the Maintenance Study

The EU-specific key secondary end points of the Maintenance Study are:

- The proportion of subjects achieving clinical remission by CDAI at Week 58
- The proportion of subjects achieving sustained clinical remission by PRO2 at Weeks 10 and 58
- The proportion of subjects achieving both clinical remission by PRO2 and endoscopic response (combined into a single end point on a patient level) at Week 58
- The proportion of subjects achieving 6-month corticosteroid-free remission by PRO2 at Week 58

The EU-specific other secondary end point of the Maintenance Study is:

- PK characteristics for filgotinib and its metabolite GS-829845

CCI

#### 8.1.4.1. Cohort A Induction Study

CCI

•

- The proportion of subjects achieving both clinical remission by PRO2 and endoscopic response (combined into a single end point on a patient level) at Week 10

• CCI

• CCI

• CCI

• CCI

• CCI

• CCI

- CCI [REDACTED]
- CCI [REDACTED]
- CCI [REDACTED]
- CCI [REDACTED]
- [REDACTED]
- █ [REDACTED]
- █ [REDACTED]
- █ [REDACTED]
- █ [REDACTED]
- █ [REDACTED]
- █ [REDACTED]
- █ [REDACTED]
- █ [REDACTED]
- █ [REDACTED]
- █ [REDACTED]
- █ [REDACTED]

8.1.4.2. Cohort B Induction Study

- CCI [REDACTED]
- █ [REDACTED]
- The proportion of subjects achieving both clinical remission by PRO2 and endoscopic response (combined into a single end point on a patient level) at Week 10
- CCI [REDACTED]

- CCI [REDACTED]
- CCI [REDACTED]
- CCI [REDACTED]
- CCI [REDACTED]
- CCI [REDACTED]
- CCI [REDACTED]
- CCI [REDACTED]
- CCI [REDACTED]

CCI [REDACTED]

- █ [REDACTED]
- █ [REDACTED]
- █ [REDACTED]
- █ [REDACTED]
- █ [REDACTED]
- █ [REDACTED]
- █ [REDACTED]
- █ [REDACTED]
- █ [REDACTED]
- █ [REDACTED]

8.1.4.3. Maintenance Study

CCI [REDACTED]

[REDACTED]

- The proportion of subjects achieving both clinical remission by PRO2 and endoscopic response (combined into a single end point on a patient level) at Week 58

- CCI [REDACTED]

- CCI [REDACTED]

- CCI [REDACTED]

- CCI [REDACTED]

- CCI [REDACTED]

- CCI [REDACTED]

- CCI [REDACTED]

- CCI [REDACTED]

- CCI [REDACTED]

CCI [REDACTED]

[REDACTED]

[REDACTED]

[REDACTED]

[REDACTED]

[REDACTED]

[REDACTED]

[REDACTED]

[REDACTED]

[REDACTED]

[REDACTED]

[REDACTED]

## 8.2. Analysis Conventions

### 8.2.1. Analysis Sets

#### 8.2.1.1. Efficacy

The primary analysis set for efficacy is the Full Analysis Set (FAS).

- The FAS for each Induction Study (Cohorts A and B) includes all randomized subjects who received at least one dose of study drug in the corresponding Induction Study (Day 1 to Week 10).
- The FAS for the Maintenance Study includes all re-randomized subjects who met the protocol definition of clinical remission by PRO2 or endoscopic response at Week 10, and received at least one dose of study drug in the Maintenance Study (Weeks 11 to 58).

Subjects will be analyzed according to the treatment group they were randomized to for the analysis period.

#### 8.2.1.2. Safety

The primary analysis set for safety analyses is the Safety Analysis Set.

- The Safety Analysis Set for each Induction Study (Cohorts A and B) includes all subjects who receive at least one dose of study drug in the corresponding Induction Study (Day 1 to Week 10).
- The Safety Analysis Set for the Maintenance Study includes all subjects who receive at least one dose of study drug in the Maintenance Study (Week 11 to 58).
- The Overall Safety Analysis Set for the study includes all subjects who received at least one dose of study drug from Day 1 to Week 58.

Subjects will be analyzed according to the study drug they actually received for the analysis period.

### 8.2.1.3. Pharmacokinetics

#### 8.2.1.3.1. Pharmacokinetic Substudy Analysis Set

The primary analysis set for intensive PK analyses will be the PK substudy analysis set for each Induction Study (Cohorts A and B), which includes all subjects in the Safety Analysis Set from the corresponding Induction Study who have enrolled into the PK substudy, and have intensive concentration data to provide interpretable results for the specific parameters of interest for the analyte under evaluation.

#### 8.2.1.3.2. Pharmacokinetic Analysis Set

The primary analysis set for general PK analyses will be defined separately for each individual study (Cohort A Induction Study, Cohort B Induction Study, and Maintenance Study). For each study, the PK analysis set includes all subjects in the corresponding Safety Analysis Set who have at least 1 non-missing plasma concentration data for filgotinib and/or its metabolite GS-829845.

CCI

### 8.3. Data Handling Conventions

Values for missing safety laboratory data will not be imputed. However, a missing baseline result will be replaced with a screening result, if available. If no pre-treatment laboratory value is available, the baseline value will be assumed to be normal (ie, no grade [Grade 0]) for the summary of graded laboratory abnormalities. If safety laboratory results for a subject are missing for any reason at a time point, the subject will be excluded from the calculation of summary statistics for that time point.

Values for missing vital signs data will not be imputed. However, a missing baseline result will be replaced with a screening result, if available.

PK concentration values and PK parameter values below the limit of quantitation (BLQ) will be presented as "BLQ" in the data listings. BLQ values that occur prior to the first dose will be treated as 0, BLQ values at all other time points will be treated as 1/2 of the lower limit of quantitation (LLOQ).

Laboratory data that are continuous in nature but are less than the LLOQ or above the upper limit of quantitation will be imputed to the value of the lower or upper limit minus or plus one significant digit, respectively (eg, if the result of a continuous laboratory test is  $< 20$ , a value of 19 will be assigned; if the result of a continuous laboratory test is  $< 20.0$ , a value of 19.9 will be assigned).

Procedures for handling missing data for CDAI, PRO2 and SES-CD (and components) will be described in the statistical analysis plan (SAP).

#### **8.4. Demographic Data and Baseline Characteristics**

Demographic and baseline measurements for each individual study (Cohort A Induction Study, Cohort B Induction Study, and Maintenance Study) will be summarized separately by treatment group using standard descriptive statistics (n, mean, standard deviation [SD], median, 1st quartile [Q1], 3rd quartile [Q3], minimum, maximum) for continuous variables and number and percentage of subjects for categorical variables.

Demographic summaries will include age, sex, race and ethnicity. Baseline characteristics may include height, weight, body mass index (BMI), SES-CD score, CDAI score, PRO2 score, number of years since diagnosis of CD, concomitant use of oral corticosteroids, concomitant use of immunomodulators, CCI, and other variables of interest.

#### **8.5. Efficacy Analysis**

##### **8.5.1. Primary Analyses**

For each Induction Study (Cohort A and Cohort B), the primary analysis will compare a filgotinib dose group to placebo on the proportion of subjects achieving clinical remission by CDAI at Week 10 and the proportion of subjects achieving endoscopic response at Week 10. In the EU, for each Induction Study (Cohort A and Cohort B), the primary analysis will compare a filgotinib dose group to placebo on the proportion of subjects achieving clinical remission by PRO2 at Week 10 and the proportion of subjects achieving endoscopic response at Week 10. Similarly, for the Maintenance Study, the primary analysis will compare a filgotinib dose group to placebo on the proportion of subjects achieving clinical remission by CDAI at Week 58 and the proportion of subjects achieving endoscopic response at Week 58. In the EU, for the Maintenance Study, the primary analysis will compare a filgotinib dose group to placebo on the proportion of subjects achieving clinical remission by PRO2 at Week 58 and the proportion of subjects achieving endoscopic response at Week 58. For a dose group to demonstrate significant treatment effect over placebo, statistical significance needs to be achieved on both clinical remission by CDAI and endoscopic response end points at significance level that is specified in Section 8.5.3. In the EU, for a dose group to demonstrate significant treatment effect over placebo, statistical significance needs to be achieved on both clinical remission by PRO2 and endoscopic response end points at significance level that is specified in Section 8.5.3.

The Cochran-Mantel-Haenszel (CMH) approach adjusting for stratification factors will be used for hypothesis testing of each primary end point within each study. For calculation of reduction from baseline in SES-CD score in the endoscopic response, SES-CD score at screening will be used as baseline value. For calculation of CDAI and PRO2 scores, refer to [Appendix 4](#).

Subjects who do not have sufficient measurements to determine efficacy end points will be considered failures (ie, non-responder imputation [NRI]). Sensitivity analyses will be described in the SAP.

### **8.5.2. Secondary Analyses**

The same statistical methods used for testing the primary end points will be utilized for testing the key secondary end points in each study (Cohort A Induction Study, Cohort B Induction Study, and Maintenance Study) separately. Subjects who do not have sufficient measurements to determine efficacy end points will be considered failures (ie, NRI).

### **8.5.3. Multiplicity Adjustments**

The graphical approach {[Bretz 2009](#)} of sequentially rejective Bonferroni-based iterative multiple test procedures will be used to control a family-wise type I error rate (FWER) at 5% (ie,  $\alpha = 0.05$ ) for hypothesis testing on co-primary and key secondary end points for each individual study (Cohort A Induction Study, Cohort B Induction Study, and Maintenance Study). This procedure strongly protects the FWER on all the primary and key secondary end points.

#### **8.5.3.1. Induction Studies (Cohorts A and B)**

The hypotheses to be tested for the induction studies are outlined below.

The primary null hypotheses to be tested:

- $H_{11}$ : The clinical remission by CDAI rate in the filgotinib 200 mg group is equal to the clinical remission by CDAI rate in the placebo group at Week 10
- $H_{12}$ : The endoscopic response rate in the filgotinib 200 mg group is equal to the endoscopic response rate in the placebo group at Week 10
- $H_{21}$ : The clinical remission by CDAI rate in the filgotinib 100 mg group is equal to the clinical remission by CDAI rate in the placebo group at Week 10
- $H_{22}$ : The endoscopic response rate in the filgotinib 100 mg group is equal to the endoscopic response rate in the placebo group at Week 10

The key secondary null hypotheses to be tested:

- $H_{13}$ : The clinical remission by PRO2 rate in the filgotinib 200 mg group is equal to the clinical remission by PRO2 rate in the placebo group at Week 10
- $H_{14}$ : The clinical response by CDAI rate in the filgotinib 200 mg group is equal to the clinical response by CDAI rate in the placebo group at Week 10
- $H_{23}$ : The clinical remission by PRO2 rate in the filgotinib 100 mg group is equal to the clinical remission by PRO2 rate in the placebo group at Week 10
- $H_{24}$ : The clinical response by CDAI rate in the filgotinib 100 mg group is equal to the clinical response by CDAI rate in the placebo group at Week 10

Each co-primary endpoint for filgotinib 200 mg compared with placebo will be tested at 2-sided 0.05 significance level first. If it fails to reject the null hypothesis for at least one co-primary endpoint, then no further formal testings will be performed. If the null hypotheses for both co-primary endpoints are rejected, testing will proceed in two sequences as describe below:

- Key secondary end points for filgotinib 200 mg compared with placebo at 2-sided 0.025 significance level in a sequential order
- Each co-primary end point for filgotinib 100 mg compared with placebo at 2-sided 0.025 significance level. If the null hypotheses for both co-primary end points are rejected, then the key secondary end points for filgotinib 100 mg compared with placebo at 2-sided 0.025 significance level will be tested in a sequential order

If all the null hypotheses within the same sequence are rejected, then the respective alpha can be passed on to the other sequence. If an end point fails to reach statistical significance within the sequence, then formal testing will stop, and only nominal significance will be reported for the remaining end points.

A graphical illustration of the testing strategy for the primary and key secondary hypotheses in the Induction Studies is shown in [Figure 8-1](#).

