- H25: The sustained clinical remission by CDAI rate in the filgotinib 100 mg group is equal to sustained clinical remission by CDAI rate in the placebo group at Weeks 10 and 58
- H26: The 6-month corticosteroid-free remission by CDAI rate in the filgotinib 100 mg group is equal to the 6-month corticosteroid-free remission by CDAI rate in the placebo group at Week 58
- H27: The sustained clinical remission by PRO2 rate in the filgotinib 100 mg group is equal to the sustained clinical remission by PRO2 rate in the placebo group at Weeks 10 and 58
- H28: The 6-month corticosteroid-free remission by PRO2 rate in the filgotinib 100 mg group is equal to 6-month corticosteroid-free remission by PRO2 rate in the placebo group at Week 58

[figure not shown]
Each co-primary end point for filgotinib 200 mg compared with placebo will be tested at 2-sided 0.05 significance level first. If it fails to reject the null hypothesis for at least one co-primary end point, then no further formal testings will be performed. If the null hypotheses for both co-primary end points are rejected, testing will proceed in two sequences as describe below:

- Key secondary end points for filgotinib 200 mg compared with placebo at 2-sided 0.025 significance level in a sequential order
- Each co-primary end point for filgotinib 100 mg compared with placebo at 2-sided 0.025 significance level. If the null hypotheses for both co-primary end points are rejected, then the key secondary end points for filgotinib 100 mg compared with placebo at 2-sided 0.025 significance level will be tested in a sequential order

If all the null hypotheses within the same sequence are rejected, then the respective alpha can be passed on to the other sequence. If an end point fails to reach statistical significance within the sequence, then formal testing will stop and only nominal significance will be reported for the remaining endp oints.

Graphical illustrations for the testing strategies for the primary and key secondary hypotheses in the Maintenance Study are shown in [Figure 8-2](#).

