- Each co-primary endpoint for filgotinib 100 mg compared with placebo at 2-sided 0.025 significance level. If the null hypotheses for both co-primary endpoints are rejected, then the key secondary endpoints for filgotinib 100 mg compared with placebo at 2-sided 0.025 significance level will be tested in a sequential order

If all the null hypotheses within the same sequence are rejected, then the respective alpha can be passed on to the other sequence. If an endpoint fails to reach statistical significance within the sequence, then formal testing will stop, and only nominal significance will be reported for the remaining endpoints.

A graphical illustration of the testing strategy for the primary and key secondary hypotheses in the Induction Studies is shown in Figure 3-1.

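### The multiplicity text passes alpha between the two dose sequences but gives no retest rule; run in parallel with the stop sentence taken literally, the passed alpha has no use

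*Protocol*

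**What the plan says.** Protocol Section 8.5.3 names the method: "sequentially rejective Bonferroni-based iterative multiple test procedures will be used to control a family-wise type I error rate" of 5% in each of the three studies. SAP Section 3.5 does the same.

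Protocol Section 8.5.3.1 then sets the order. The gate is the pair of 200 mg co-primaries: "Each co-primary endpoint for filgotinib 200 mg compared with placebo will be tested at 2-sided 0.05 significance level first". If both are rejected, two sequences open. One is "Key secondary end points for filgotinib 200 mg compared with placebo at 2-sided 0.025 significance level in a sequential order". The other is the 100 mg co-primaries, each at 2-sided 0.025, and then the 100 mg key secondaries at 2-sided 0.025.

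Two adjacent sentences close the description. The first is "If all the null hypotheses within the same sequence are rejected, then the respective alpha can be passed on to the other sequence". The second is "If an end point fails to reach statistical significance within the sequence, then formal testing will stop, and only nominal significance will be reported", which applies to the end points that remain.

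The same pair of sentences stands in the EU induction text (Section 8.5.3.1.1) and in both Maintenance texts (Sections 8.5.3.2 and 8.5.3.2.1), for example "If an end point fails to reach statistical significance within the sequence, then formal testing will stop and only nominal significance will be reported". SAP Section 3.5.1.1 repeats it ("If an endpoint fails to reach statistical significance within the sequence, then formal testing will stop"), and SAP Sections 3.5.1.2, 3.5.2.1 and 3.5.2.2 refer back to that approach. One wording therefore governs Cohort A, Cohort B and Maintenance, in the EU and the non-EU families.

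Neither document states the level a sequence holds after it receives alpha, or whether a hypothesis missed at 0.025 is tested again.

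**The concern.** A sequence gains from passed alpha only if one of its hypotheses missed 0.025; a sequence that keeps rejecting at 0.025 does not need more. If both sequences run at 0.025 and the stop sentence is applied as it stands, the sequence that needs the alpha is closed before the alpha arrives, and the passing sentence does nothing. The cited graphical procedure works differently: it retests the first unrejected hypothesis at the enlarged level.

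The issue decides whether 100 mg can carry a confirmatory claim when its co-primaries fall between 0.025 and 0.05 and all 200 mg key secondaries are rejected at 0.025. If the reading is chosen once p-values are known, that claim rests on a post hoc choice.

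**Working it through.** **1. Three readings of the text.** In all three I take the stop as confined to the sequence in which the failure occurs.
- *Literal parallel*: both sequences run at 0.025, and a failure is final.
- *Graphical retest*: a sequence that fails at 0.025 is retested at 0.025 + 0.025 = 0.05 if the other is fully rejected.
- *200 mg first*: the 200 mg key secondaries are tested first; 100 mg is then tested once, at 0.05 if they were all rejected and at 0.025 otherwise.

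**2. Where they part.** Illustrative p-values, with the 200 mg co-primaries already rejected:

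| 200 mg key secondaries | 100 mg co-primaries | Literal parallel | Graphical retest | 200 mg first |
|---|---|---|---|---|
| 0.01, 0.01 | 0.03, 0.01 | 100 mg nominal only | 100 mg rejected | 100 mg rejected |
| 0.04, 0.01 | 0.03, 0.01 | 100 mg nominal only | 100 mg nominal only | 100 mg nominal only |
| 0.04, 0.01 | 0.01, 0.01 (key secondaries also 0.01) | 200 mg secondaries nominal | 200 mg secondaries rejected | 200 mg secondaries nominal |

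Row 1 is the case at issue. In row 2 no reading gives 100 mg a claim, and that is correct. Row 3 shows that the gap also affects alpha flowing from 100 mg to 200 mg.

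**3. Error rate.** In a simulation with 400,000 replicates and independent test statistics, the largest family-wise error over the null configurations tried was 0.0488 without recycling and 0.0503 with graphical retest, that is 5% within simulation error.

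**4. The plan's own power.** Inputs from protocol Section 8.9.1: n = 220 per arm, CDAI remission 45% v 25%, endoscopic response 25% v 10%. For each end point, with p̄ the mean of the two rates,

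power = Φ{ [ |p1 − p0| − z(1−α/2)·√(2p̄(1−p̄)/n) ] / √( p1(1−p1)/n + p0(1−p0)/n ) }.

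At α = 0.05 for 200 mg, CDAI gives Φ{(0.200 − 1.960 × 0.0455)/0.0445} = 0.994 and endoscopic response gives 0.987. The product is 0.981, or 0.974 with continuity correction; the plan states 97%.

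**5. 100 mg co-primaries at the two levels.** The documents give no 100 mg effect for this calculation, so I take a share s of the 200 mg effect: CDAI 25% + s × 20 points, endoscopic response 10% + s × 15 points. Products of the two powers, from the same formula:

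| s | α = 0.025 | α = 0.05 | Gap |
|---|---|---|---|
| 1/2 | 0.519 × 0.517 = 0.268 | 0.630 × 0.628 = 0.395 | 0.127 |
| 2/3 | 0.780 × 0.759 = 0.592 | 0.855 × 0.838 = 0.716 | 0.124 |
| 4/5 | 0.911 × 0.887 = 0.808 | 0.949 × 0.932 = 0.884 | 0.077 |
| 1 | 0.986 × 0.974 = 0.960 | 0.994 × 0.987 = 0.981 | 0.020 |

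**6. Chance that the alpha is passed.** The 200 mg co-primaries and both 200 mg key secondaries must succeed. For the latter I use PRO2 remission 30% v 15% (Section 8.9.1.1) and CDAI response 59% v 41% (the Phase 2 rates in Section 1.3.2). At 0.025 their powers are 0.940 and 0.941, product 0.884. With the gate, 0.884 × 0.981 ≈ 0.87.

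**7. Loss.** Roughly 0.87 times the gap: 0.11, 0.11, 0.07 and 0.02. A simulation with the shared placebo arm gives the probability that both 100 mg co-primaries are formally declared, literal stop v retest:
- independent end points: 27% v 39%, 60% v 71% and 81% v 87% at s = 1/2, 2/3 and 4/5;
- correlation 0.5 between end points: 31% v 43%, 62% v 72% and 82% v 87%;
- equal effect (s = 1): a loss of about 1 to 2 points.

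Repeat runs moved single figures by about one point. The full procedure was not computed for the EU families or for Maintenance.

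**The case against.** The best defence is that the stop sentence names no level. Section 8.5.3.1 says only that testing proceeds in two sequences, not that they run at the same time. The passing rule is explicit and the governing method is named. Read together, a hypothesis fails only at the level its sequence finally holds. A reading that empties the preceding sentence and departs from the cited method is not the natural one. The testing figures (protocol Figures 8-1 to 8-3, SAP Figures 3-1 to 3-4) are not shown in the copy reviewed, and in a graphical procedure the graph is part of the specification.

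Much of this stands. A reader might infer that the plan disables recycling, so that the passed alpha can never be used. The documents do not support that: if the 200 mg sequence is completed first, 100 mg is tested at 0.05 without a prior failure and both sentences operate. Nor does every 100 mg p-value between 0.025 and 0.05 lose a legitimate claim; that needs all 200 mg key secondaries rejected at 0.025. There is also no inflation of the error rate.

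The defence does not remove the gap. Every level written in the two sequences is 0.025. Nothing says that a missed hypothesis is tested again, and nothing puts the 200 mg sequence first. Reading 200 mg first would also block alpha from 100 mg to 200 mg, which the passing sentence allows. Citing the graphical method does not say which text prevails where the prose and the method differ.

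The size is conditional too. It rests on an assumed 100 mg effect and does not carry over to Maintenance, where the non-EU family needs six 200 mg key secondaries rejected before alpha passes.

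**Conclusion.** The point holds as an ambiguity with consequences. The text allows readings that give opposite formal conclusions from the same data, and the literal parallel reading departs from the procedure the plan names. They differ only when one sequence is fully rejected at 0.025 and the other has a hypothesis with p between 0.025 and 0.05. The cost is power and pre-specification, not type I error.

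For non-EU induction the literal stop costs the 100 mg co-primaries about 6 to 12 points of power per cohort if the 100 mg effect is 1/2 to 4/5 of the 200 mg effect, and about 1 to 2 points at equal effect. This rests on the plan's 200 mg and placebo rates, the Phase 2 CDAI response rates and the assumed 100 mg share. It should be settled before unblinding; whether the figures already show the intended flow could not be checked.

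**What to change.** Replace the stop sentence in protocol Sections 8.5.3.1, 8.5.3.1.1, 8.5.3.2 and 8.5.3.2.1 and in SAP Section 3.5.1.1, on which Sections 3.5.1.2, 3.5.2.1 and 3.5.2.2 rely. Proposed text:

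> If a hypothesis is not rejected at the level its sequence currently holds, testing pauses in that sequence only. If the other sequence is fully rejected, its 0.025 is added and the paused sequence is retested from its first unrejected hypothesis (both 100 mg co-primaries where applicable) at 2-sided 0.05. Remaining end points are nominal only once no further alpha can be passed.

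Check it against protocol Figures 8-1 to 8-3 and SAP Figures 3-1 to 3-4, and date it before unblinding. The cost is a few sentences in the SAP and a matching protocol clarification. It needs no patients, data or extra alpha, because this is the procedure already cited.
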